Some subgroups of the US population, including long-term care workers (LTCWs), have higher rates of COVID-19 vaccine hesitancy⁵. LTCWs include people who work in long-term care facilities or home-based care, and include roles such as certified nurse assistants, residential care assistants and non-clinical support. Although long-term care facilities have been epicenters of COVID-19 outbreaks, warranting widespread vaccination, there is reported low vaccination coverage among LTCWs^{12,13}. LTCWs usually serve those most vulnerable to serious complications of COVID-19¹⁴. LTCWs are also likely to be more vulnerable to complications of COVID-19 themselves. More than 50% of LTCWs are from minority and socioeconomically disadvantaged groups, often working multiple jobs^{15,16}. Given the vulnerability of the populations they serve, the possibility of transmission in their local communities, and their own increased risk of COVID-19 morbidity/mortality, it is important to increase COVID-19 uptake among LTCWs. In August 2021, the US Federal Government announced its intent to impose a mandate that LTCWs be vaccinated in order to be eligible to work. This mandate has now been expanded to include employees in all health facilities that receive federal funding. The Centers for Medicare and Medicaid (CMS), working with the Centers for Disease Control and Prevention

(CDC), will be responsible for imposing the broad mandate and planned to release an interim rule in October 2021.

While vaccine mandates have clear, positive implications for reducing COVID-19 spread and disease severity, other potential consequences should not be overlooked. At the forefront are job losses and workforce shortages if workers do not adhere to mandates, and reduced workplace trust and increased vaccine hesitancy¹⁷. The likely legal challenges and conflict created between management and employees may also have a damaging impact on relationships at work and the wellbeing of long-term care workers. These consequences highlight the importance of efforts to increase confidence in the COVID-19 vaccines, so decisions to vaccinate are made willingly. Increasing vaccine confidence will also help alleviate the concerns of those already vaccinated, but still hesitant to follow future vaccination recommendations.

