4.3 Participants

4.3.1 Randomized Controlled Trial (Aims 1 and 2)

Eligible participants will include vaccinated and unvaccinated LTCWs who self-identify as: 1) being 18 years and older, 2) living in the United States, 3) having worked in a long-term care setting in the past two years, 4) able to verify their LTCW status, 5) not currently pregnant or breastfeeding, and 6) able to read, write, and understand English, and 7) being at least somewhat worried about the COVID-19 vaccines and/or not having received any COVID-19 booster vaccine (see Table 2).

Eligible LTC settings will include nursing homes, skilled nursing facilities, assisted living facilities, home health care, hospice care, and retirement communities. The two-year timeframe will avoid excluding those who are currently unemployed, and will approximately cover the duration of time since the COVID-19 pandemic began. To ensure a high proportion of study participants represent our low confidence target group, we will use two criteria – worry about the vaccines and booster uptake – to screen participants for eligibility. These criteria are based on a preliminary analysis of panel survey data, which found associations between booster intent, worry about the vaccines, and vaccine confidence.

Table 2. Screening questions and eligibility criteria

Question	Eligible Response(s)	Ineligible Response(s)
Can you read, write, and understand English? (adapted from ³⁶)	Yes	No
How old are you?	18-19 years; 20-24 years; 25-29 years; 30-34 years; 35-39 years; 40-44 years; 45-49 years; 50-54 years; 55-59 years; 60-64 years; 65 years or older	Less than 18
Do you live in the United States?	Yes	No
This study is for long-term care workers. We must be sure that everyone who joins is giving us the correct information about who they are. We also need to be sure that everyone has worked in a long-term care setting. It is important to our study results. The information that you provide in this survey will help us confirm your identity and that you are a long-term care worker. We will never contact your employer about your participation in the study.	N/A	N/A
Have you worked in a long-term care setting in the past 2 years? This includes nursing homes, skilled nursing facilities, assisted living facilities, home health care, hospice care, and retirement communities.	Yes	No

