Below is a list of ways we can confirm you have worked in a long-term care setting in the past 2 years. Which of these can you do? Select all that apply. We will ask you to complete one of these options later in the survey.	Provide information from your workplace ID badge; Provide your Certification or Professional License Number; Email us from your work email account; Provide information from a recent pay stub (within the last 2 years);	None of the above
Are you pregnant or breastfeeding	No	Yes
Are you worried about the COVID-19 vaccines? If you have completed your initial COVID-19 vaccine series (1 Johnson & Johnson shot or 2 Pfizer/Moderna shots), have you had at least one booster shot since then?	Somewhat; Very OR No, I have not had any booster shots; I have not completed my initial series	Not at all; A little; AND Yes, I have had at least one booster shot; Not sure

4.3.2 Aim 3

Eligible participants for Intervention Consultations (as described in Table 1) will include LTCWs, including those who are members of our Stakeholder Advisory Group. We anticipate interviewing 10-12 participants for each round of consultations, until we reach thematic saturation.³²

For Implementation Consultations (as described in Table 1), our participants will be trial participants, study team members, and other key stakeholders identified through the “Adopters Implementers and Maintainers” brainstorm who may play roles in facilitating implementation in both the trial and sustainability phases. Reporting of Aim 3 activities will adhere to the Consolidate Criteria for Reporting Qualitative Research (COREQ) checklist³⁷.

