What else do I need to know?	If you do not want a vaccine now but change your mind later, you can get it then.	
 After at least 5 months, most people 5 years or older should get a booster shot. Some people may get a second booster at least 4 months after their first. The vaccine cannot give you COVID-19. The vaccine cannot change your DNA. There is no microchip in the vaccine. If you have had COVID-19, the vaccine may still lower your risk of getting it again. 	
 After at least 2 months, most adults should get a booster shot. Some people may get a second booster at least 4 months after their first. The vaccine cannot give you COVID-19. The vaccine cannot change your DNA. There is no microchip in the vaccine. If you have had COVID-19, the vaccine may still lower your risk of getting it again.

Definitions:

Rare side effects or harms

These may include: Guillain Barré syndrome, blood clots with low platelets, and heart inflammation. COVID-19 can cause similar problems.

Guillain Barré syndrome

This is an inflammation of the nerves that may need hospital care. Most people get better, but full recovery can take a year or more.

Many people have seen numbers about how much vaccines can lower the risk of getting COVID-19. Sometimes, these numbers seem different between vaccines. Trying to compare these numbers is not a fair scientific comparison and could mislead. That is why this decision aid does not show these numbers.

DynaMed Decisions' Option Grid™ decision aids are reviewed on an ongoing basis and updated to reflect the latest evidence. Last Update: May 19, 2022

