- *Likelihood of recommending COVID-19 vaccination (others not vaccinated)*. This question will be evaluated using a Net Promoter Score (NPS) approach, adding one for each positive response, zero for neutral, and subtracting one for each negative response, then dividing by the number of non-missing responses for each trial arm. NPS values will be compared using Wald intervals [1].
- *Likelihood of recommending COVID-19 booster vaccination (coworker)*. This question will be evaluated using the NPS approach, described above.
- *COVID-19 vaccine uptake (any dose)*. This will be evaluated as a binary classifier compared across trial arms using two-proportion z-tests.
- *COVID-19 vaccine uptake (initial series completion)*. For participants who have received any dose of a COVID-19 vaccine, this will be evaluated as a binary classifier compared across trial arms using two-proportion z-tests.
- *COVID-19 vaccine uptake (booster completion)*. For participants who have completed their initial vaccine series, this will be evaluated as a three category variable (No, Not sure, Yes) compared across trial arms using chi-squared tests.
- *COVID-19 vaccine intent (initial series)*. For participants who are unvaccinated, we will assess their intentions of getting a COVID-19 vaccine, this will be evaluated using the Net Promoter Score approach, where the three responses – Yes, Not Sure, No – will be evaluated as analogous to promoter, neutral, and detractor, respectively. The question will be evaluated using the NPS analysis, described above.
- *COVID-19 vaccine intent (booster)*. For participants who have completed an initial vaccine series, this will be evaluated using the Net Promoter Score approach, where the three responses – Yes, Not Sure, No – will be evaluated as analogous to promoter, neutral, and detractor, respectively. The question will be evaluated using the NPS analysis, described above.
- *COVID-19 vaccine intent (future vaccine recommendations)*. Participants' intent to get COVID-19 vaccines regularly in the future if they are recommended will be evaluated using the Net Promoter Score approach, where the three responses – Yes, Not Sure, No – will be evaluated as analogous to promoter, neutral, and detractor, respectively. The question will be evaluated using the NPS analysis, described above.

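### As defined, no uptake outcome can register a further dose in workers already boosted at baseline, whom the trial enrolls when they are worried

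*Combined protocol and SAP*

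**What the plan says.** Section 4.3.1 makes a worker eligible on either of two grounds: "being at least somewhat worried about the COVID-19 vaccines and/or not having received any COVID-19 booster vaccine". Table 2 confirms that both conditions must fail before a person is screened out, since the ineligible combination reads "Not at all; A little; AND Yes, I have had at least one booster shot; Not sure". The booster part of the screener asks "have you had at least one booster shot since then" and does not count boosters.

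Section 4.5.2 measures uptake with four questions written by the study team, whose wording is not reproduced. Table 3 assigns one to any dose, two to initial series completion and one to booster completion. Appendix B analyzes them as follows:

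- Any dose: "This will be evaluated as a binary classifier compared across trial arms using two-proportion z-tests".
- Initial series completion: "For participants who have received any dose of a COVID-19 vaccine, this will be evaluated as a binary classifier".
- Booster completion: "For participants who have completed their initial vaccine series, this will be evaluated as a three category variable (No, Not sure, Yes", compared by chi-squared test.

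Appendix B places these cross-sectional analyses at T1 (3 weeks). T2 and T3 enter only through change from baseline, which scores one for a higher value and zero for the same or a lower one. Baseline vaccination status is among the listed moderators of the primary and secondary outcomes.

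**The concern.** Worried workers who already have a booster are in the trial by design, and the background gives a reason for wanting them there: "Increasing vaccine confidence will also help alleviate the concerns of those already vaccinated, but still hesitant to follow future vaccination recommendations". A further dose was a real possibility for them. The conversation aid in Appendix A states: "Some people may get a second booster at least 4 months after their first". Four months is shorter than the 6-month follow-up, so some participants boosted before T0 could reach that interval while under observation.

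Yet the uptake outcomes stop at the first booster. Under the scoring rules, a boosted worker who takes another dose after the intervention looks the same as one who declines it. At stake is whether the uptake results say anything about behavior in this group, and how far its presence blurs the result for everyone else.

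**Working it through.** **The plan's own figure.** The documents give no power or sample size for uptake. The only power statement (section 4.6) concerns the Vaccine Confidence Index: 600 per arm, 8 points, 80%, two-sided 0.05. The control rate is not given. A pooled-variance two-proportion z-test at the least favorable rates, 46% versus 54%, gives power 0.792 (613 per arm would be needed for 0.80). The figure reproduces, but it does not bear on uptake.

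**Tracing a worried participant boosted before T0.** The screener's booster question is put to people who have completed the initial series, so a Yes to it implies a Yes lower down.

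| Outcome | Value at T0 | Highest possible later value | Change score |
|---|---|---|---|
| Any dose | Yes | Yes | 0 |
| Initial series completion | Yes | Yes | 0 |
| Booster completion | Yes | Yes | 0 |

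With consistent answers, such a person contributes a fixed Yes to each cross-sectional comparison and a fixed 0 to each change-from-baseline comparison, in every arm. An arm-by-status effect on uptake cannot be estimated in a stratum where the outcome takes only one value, so the moderator analysis yields nothing there.

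**Dilution of the booster comparison.** Let s be the share boosted at T0, p the rate of new boosting among the rest under control, and d the gain from an arm among the rest.

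- Cross-sectional rates: s + (1 − s)p versus s + (1 − s)(p + d)
- Change-from-baseline rates: (1 − s)p versus (1 − s)(p + d)
- Difference in both cases: (1 − s)d

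The documents give none of s, p or d. The table assumes p = 10% and d = 8 points, with 600 per arm all in the comparison, no loss to follow-up and a two-sided 0.05 test. Booster completion is in fact analyzed only among series completers, so actual numbers would be smaller.

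| s | Able to change, per arm | Difference (points) | Power, cross-sectional | Power, change from baseline | Power, only those not boosted at T0 |
|---|---|---|---|---|---|
| 0% | 600 | 8.0 | 0.980 | 0.980 | 0.980 |
| 10% | 540 | 7.2 | 0.847 | 0.965 | 0.967 |
| 25% | 450 | 6.0 | 0.584 | 0.925 | 0.934 |
| 50% | 300 | 4.0 | 0.287 | 0.776 | 0.808 |
| 75% | 150 | 2.0 | 0.132 | 0.470 | 0.515 |

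At s = 50%, for example, the cross-sectional rates are 0.5 + 0.5 × 0.10 = 55% and 0.5 + 0.5 × 0.18 = 59%. The change-from-baseline rates are 5% and 9%. Varying p from 5% to 20% at s = 50%, cross-sectional power stays at 0.285 to 0.297. Change-from-baseline power falls from 0.918 to 0.568, and power in those not boosted falls from 0.930 to 0.631.

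The table concerns an effect among people not yet boosted. Any effect on further doses among the boosted is not diluted but absent from every column.

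**The case against.** The strongest reply is that the instrument is not shown. A reader might infer that the trial cannot record a further dose at all. The documents do not support that: the follow-up booster question could be worded differently from the screener, and the contextual-factors item, asked at T0 to T3 and covering personal experience with the vaccines, might pick up a further dose incidentally. What stands is that no prespecified uptake outcome is defined to use such information.

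A reader might also infer that the trial cannot answer its own question about continuing adherence. No research question, aim or hypothesis asks about repeat doses; the references to scheduled boosters and future recommendations are background rationale. Nor are boosted participants uninformative in general. Confidence, both recommendation scores, feeling informed, misinformation identification, trust and future-vaccine intent can all move in them, and the last is asked of everyone. But intent is not receipt of a dose.

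Third, the consequences are bounded. Uptake is secondary, and Appendix B reads secondary results as directional trends without a corrected threshold. Since baseline vaccination status is a planned moderator, an effect among those who can still change can be examined separately. This meets much of the dilution problem, provided the result is reported that way, but it supplies no data on further doses.

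Finally, the documents do not say how many boosted participants could have been offered another dose, and the conversation aid shown is a May 2022 version noted as since updated. This limits what can be said about size, not about the definitions.

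**Conclusion.** The point holds for the outcomes as defined. Participants already boosted at T0 cannot register a further dose on any prespecified uptake outcome. They add a constant to both forms of the booster comparison and leave the moderator analysis of uptake empty in their stratum. This rests on reading the booster item as at least one booster. The screener supports that reading, as does section 4.5.2, which directs the initial-series and booster intent questions to people not yet vaccinated or boosted.

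The dilution factor is (1 − s), but the documents do not give s. It is tempting to quote a specific number of points lost; any such number, including those in the table, is an illustration on assumed inputs. The primary outcome and the remaining secondary outcomes are unaffected. This is a worthwhile, inexpensive improvement to a secondary endpoint, not a threat to the trial's main conclusion.

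**What to change.** 1. Add one cumulative item to the remaining follow-up surveys, asking whether the participant has received any COVID-19 vaccine dose since joining the study. If an existing item already captures this, name it in Appendix B instead. Because the item is cumulative, one answer at T3 covers the whole period.
2. Add a secondary outcome, any new dose since randomization, compared by arm overall and by T0 status (unvaccinated, series without booster, boosted).
3. State its analysis set. Section 4.4.2 shows that data collection had already begun, so analyze it among participants surveyed after the item was introduced. Do not impute it for those who finished earlier, and exempt it to that extent from the missing-data rule in Appendix B. Say how this set relates to the requirement of valid primary outcome data at both T0 and T1. Introducing the item on the same date in all arms keeps the comparison a randomized one, apart from attrition.
4. Report the existing booster-completion comparison also among those not boosted at T0. This needs no new data.

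The cost is a short amendment, a slightly longer survey, and a smaller sample for the new outcome than for the others.

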4.8 Statistical Analysis

4.8.1 Data Source Accuracy

Initial examination of data will include descriptive statistics and frequency distributions in order to check planned analysis assumptions, identify missing data, and check data source adequacy. This process will also inform any necessary variable re-coding prior to data analysis.

4.8.2 Analyses Corresponding to Trial Aims 1 and 2

All analyses pertaining to study Aims 1 and 2 will be conducted on an intention-to-treat (ITT) basis (i.e. the arm participants were assigned to) and as-treated basis (i.e. whether they engaged with their assigned intervention or control). A detailed data analysis methodology, including planned statistical tests, timepoints for outcome assessment, and treatment of missing data, is included in Appendix B.

For Aim 1, hypothesis 1.1, we will conduct one-tailed tests (superiority analysis) to compare the impact of each of the two intervention arms against the enhanced usual practice arm on primary and secondary outcomes. For Aim 1, hypothesis 1.2, we will conduct a two-tailed test (equivalence analysis) of primary and secondary outcomes between the two intervention arms. While we hypothesize that the dialogue-based webinar intervention (Arm 1) will be superior to the social media website intervention (Arm 2), a finding of superiority, inferiority, or no distinguishable difference will be a valuable finding.

For Aim 2, hypothesis 2.1, our mediation analyses seek to identify the relationship between the interventions, mediator variables, and primary and secondary outcomes. We are interested in whether interventions operate through the mediator rather than directly affecting the outcome. If the results for Aim 1 are non-significant, we will determine whether it is a null effect of the intervention on the mediator or a null effect of the mediator on the outcome. We will determine mediation strength and mechanism generalizability by comparing effects across subgroups.

For Aim 2, hypothesis 2.2, our exploratory moderation analyses (also referred to as heterogeneity of treatment effects (HTE) analyses) seek to understand whether certain participant characteristics and beliefs influence the relationship between the interventions and vaccine confidence, as well as other secondary outcomes. We will explore moderators including (but not limited to) vaccination status, religious beliefs, age, race, ethnicity, perceived influence of others, and personal experiences with COVID-19.

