- *Feeling informed about the COVID-19 vaccines*. The degree to which participants' feel informed about the COVID-19 vaccines (have enough information and understand that information) will be evaluated using a continuous variable, calculated as the mean scale

score across two items ((1) having enough information, (2) understanding the information) for each participant. The mean of all mean scores will be compared across trial arms with two-sample unpaired t-tests.

- *Identification of COVID-19 vaccine information and misinformation.* Subjects' identification of COVID-19 vaccine information and misinformation will be scored on a scale of zero to four and treated as a continuous linear variable. Results will be compared across trial arms with two sample unpaired t-tests.
- *Trust in COVID-19 information from different sources.* Subjects' trust in COVID-19 information from different sources will be evaluated using a continuous variable, calculated as the mean scale score across three items for each participant. The mean of all mean scores will be compared across trial arms with two-sample unpaired t-tests.
- *Change from baseline in secondary outcomes.* Change from baseline will be scored as a binary variable with an increased value scored as one and a no change or decreased value scored as zero. For each evaluation after baseline, each arm will be compared using two-proportion z-tests. For vaccine and booster intent questions, where the intent question is not repeated if the participant indicates an increase in vaccination status, intent will be imputed from uptake. To be clear, an individual who is unvaccinated at T0, then returns at T1 and indicates that he or she is now vaccinated, will be presented with the vaccine intent question at T0 but not at T1. Because the individual is now vaccinated, asking about vaccine intent at T1 would be confusing. For analyzing change in vaccine intent, the individual whose vaccine status increases would be considered to have positive intent at T1. A similar approach will be used for booster intent.
- *As treated analysis of primary and secondary outcomes.* Primary and secondary outcome analyses will be repeated, limited to the as treated samples.

Aim 2

To determine if LTCWs' characteristics and other factors mediate and moderate the interventions' impact on vaccine confidence and other secondary outcomes.

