The primary outcome involves three separate tests, one a two-tailed equivalence test and two one-tailed superiority tests. In order to achieve a family-wise error rate less than 0.050, the Bonferroni method was employed to set a p-value threshold at 0.016 for each of the three primary outcome analyses. For each comparison, mean-value separation will be considered significant based on a 98.4% confidence interval, which translates to +/- 2.45 times the standard

error for the sample mean for the equivalence test and greater than 2.15 times the standard error for the superiority analyses.

Based on the high number of secondary outcome analyses (cross-sectional T1; change from baseline; ITT; as-treated), results data for these outcomes will be viewed in more aggregate form as trending in one direction or not, rather than adopting a specific Bonferroni-corrected p-value threshold.

References

1. B. Rocks, Interval Estimation for the “Net Promoter Score.” *Am. Stat.* 70, 365–372 (2016).
2. R. M. Baron, D. A. Kenny, The moderator–mediator variable distinction in social psychological research: Conceptual, strategic, and statistical considerations. *J. Pers. Soc. Psychol.* 51, 1173–1182 (1986).
3. T.E. Raghunathan, J.M. Lepkowski, J. Van Hoewyk, P. Solenberger, et al. A multivariate technique for multiply imputing missing values using a sequence of regression models. *Surv. Methodol.* 27, 85–96 (2001).

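### The chi-squared test for booster completion has no direction, so it cannot give the one-tailed comparison planned in section 4.8.2, and it can respond to a No/Not sure shift alone

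*Combined protocol and SAP*

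**What the plan says.** For Aim 1, section 4.8.2 states: "we will conduct one-tailed tests (superiority analysis) to compare the impact of each of the two intervention arms against the enhanced usual practice arm". It applies this to secondary as well as primary outcomes, and plans a two-tailed comparison of Arm 1 with Arm 2.

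The Secondary outcomes list in Appendix B then gives a test for each outcome:

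- Uptake, any dose: "This will be evaluated as a binary classifier compared across trial arms using two-proportion z-tests". Initial series completion gets the same treatment among those with any dose.
- Uptake, booster completion: among those who completed the initial series, a "three category variable (No, Not sure, Yes) compared across trial arms using chi-squared tests". The text does not say whether arms are compared in pairs or all three together.
- The three intent items have the same Yes/Not sure/No responses, but are scored in order as promoter, neutral and detractor.
- Change from baseline in secondary outcomes is binary, with "an increased value scored as one and a no change or decreased value scored as zero", and is compared by two-proportion z-tests.

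Under Multiple testing, Appendix B sets no p-value threshold for secondary outcomes: "results data for these outcomes will be viewed in more aggregate form as trending in one direction or not".

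**The concern.** A Pearson chi-squared test on three unordered categories asks whether the response distributions differ in any way. It does not ask whether more people in the intervention arm are boosted. This has two consequences.

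- The statistic is the same whether the intervention raises or lowers boosting, so the one-tailed comparison of section 4.8.2 cannot be read from it.
- A move between No and Not sure counts as a difference even when the share answering Yes is identical.

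The other two uptake outcomes do not have this problem, and the plan gives no reason for treating booster completion differently. The outcome matters here because eligibility rests partly on not having had a booster.

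**Working it through.** **Inputs.** From section 4.6: 600 per arm, and 360 per arm after 40% attrition (600 × 0.6). Booster completion is analysed only among those who completed the initial series. Their number is not stated and cannot exceed the arm size, so 360 and 600 are upper bounds. The category rates are not in the documents, so all rates below are assumptions, and 0.05 is used only as a yardstick.

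**The plan's own power figure.** None is given for the booster test. The stated 80% power (8 points, 600 per arm, two-sided 0.05) concerns the primary outcome. With a pooled-variance two-proportion formula it comes out at 79.2% to 81.2% for control rates of 35% to 50%, so the method agrees with the plan.

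**1. Equal boosting, small p-value.** Take 360 per arm with No/Not sure/Yes of 180/36/144 and 198/18/144, so Yes is 40% in both. The expected counts per arm are 189, 27 and 144.

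χ² = 2 × 9²/189 + 2 × 9²/27 + 0 = 0.857 + 6.000 = 6.857

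On 2 df, p = exp(−6.857/2) = 0.032. A z-test on Yes would give exactly zero difference.

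**2. How often this happens.** Power comes from the noncentral chi-squared distribution on 2 df with λ = n Σ (p_ij − p̄_j)²/p̄_j, summed over two arms and three categories. Not sure is halved, Yes is equal in both arms, and Yes ranges from 20% to 42%:

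| Not sure, from → to | 360 per arm | 600 per arm |
|---|---|---|
| 10% → 5% | 63-65% | 85-87% |
| 5% → 2.5% | 34% | 52-53% |
| 3% → 1.5% | 21% | 33% |

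For the first row with Yes at 40% and 360 per arm, a 20,000-run simulation gave 64.6% for the chi-squared test and 5.1% for a one-sided z-test on Yes.

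**3. No direction.** With Yes at 45% against 37% and 360 per arm, the chi-squared test rejects in 49.9% of trials. With the arms exchanged, so that benefit becomes harm, it is again 49.9%.

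**4. Power for an 8-point rise in Yes, 360 per arm, α = 0.05.**

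| Control → intervention (No, Not sure, Yes) | 2-df χ² | Two-sided z, Yes | One-sided z, Yes |
|---|---|---|---|
| .60,.10,.30 → .52,.10,.38 | 54% | 62% | 73% |
| .50,.08,.42 → .42,.08,.50 | 50% | 58% | 70% |
| .75,.05,.20 → .67,.05,.28 | 62% | 71% | 81% |
| .60,.10,.30 → .56,.06,.38 | 69% | 62% | 73% |

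In the first three rows the whole gain comes from No. At equal sidedness the third category then costs about 7 to 10 points. In the last row half the gain comes from Not sure, and the three-category test is ahead of the two-sided binary test by about 7 points.

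**The case against.** The strongest reply is that little depends on this p-value. Secondary outcomes have no threshold and are read by direction of trend, and the arm percentages would show which way Yes moved. That stands, and it keeps the point minor. It does not remove the inconsistency, since an undirected statistic is a poor source for a judgement about direction.

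A second reply is that the change-from-baseline analysis is binary and directional. This is partly right. That analysis does not say where Not sure ranks, so a move from No to Not sure might be scored as an increase.

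Third, the frequency of Not sure may be low. Table 2 makes a Not sure booster answer ineligible unless the person is also somewhat or very worried, which limits that group at entry. This is fair and is why the range goes down to 3%.

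A reader might infer two stronger points, and the documents support neither:

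- **Inflated false-positive error.** In the scenarios of step 2 the response distributions truly differ, so the chi-squared test is not in error. It answers a different question, and the plan has no significance rule for this outcome.
- **A general power loss of about 20 points.** That comes from setting the 2-df test (50-62%) against a one-sided test (70-81%). About 10 to 12 points of the gap is sidedness, and no document sets one-sided 0.05 for secondary outcomes. The remainder can reverse, as the last row of step 4 shows.

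**Conclusion.** The inconsistency is real and minor. As written, the booster test cannot deliver the one-tailed intervention-versus-control comparison planned for secondary outcomes, and a shift between No and Not sure can give a small p-value with no change in boosting. How often depends on an unstated Not sure rate and an unstated number of initial-series completers. Over the assumed rates of 3% to 10%, with the rate halved, it ranges from about 21% to 87%, and the sample sizes behind those figures are upper bounds. The lack of direction depends on neither quantity. The one-tailed plan concerns only the two comparisons with enhanced usual practice; Arm 1 against Arm 2 is two-tailed.

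**What to change.** Replace the booster sentence in Appendix B. Among initial-series completers, define booster completion as Yes against No/Not sure. Compare arms in pairs with two-proportion tests, one-tailed for each intervention against enhanced usual practice and two-tailed for Arm 1 against Arm 2, and report the risk difference with its interval. Show the three-way table as description, and add a sensitivity analysis that excludes Not sure.

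The cost is about a sentence of the SAP and no new data. The one drawback is that pooling counts people of unknown status as not boosted, which the sensitivity analysis addresses.
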